2.2 Study Design and Dose Rationale

2.2.1 Study Design

This is a randomized, open-label, comparative study on enzalutamide and flutamide.

Patients with M0 or M1 castration-resistant prostatic neoplasm that relapsed during CAB therapy with bicalutamide will be randomized to Group A or B. Dynamic allocation will be performed with minimization with biased coin technique. The following stages (M0/N0, M0/N1, or M1) will be used as allocation factors.

- M0/N0: No distant metastasis, and no lymph node metastasis
- M0/N1: Without distant metastasis, but with metastasis in lymph nodes distal to the aortic bifurcation
- M1: With distant metastasis (including metastasis in lymph nodes proximal to the aortic bifurcation)

For subjects in Group A, enzalutamide is administered as the 1st line AAT. After the confirmation of PSA progression, medication is changed from enzalutamide to flutamide as the 2nd line AAT. For subjects in Group B, flutamide is administered as the 1st line AAT. After the confirmation of PSA progression, medication is changed from flutamide to enzalutamide as the 2nd line AAT. The treatment period with each drug should not be more than 2 years from the enrollment of the last subjects.

PSA progression will be defined according to the consensus guidelines of PCWG2. For patients with PSA declines at Week 13, the PSA progression date is defined as the date that a $\geq 25\%$ increase and an absolute increase of ≥ 2 ng/mL above the nadir is documented, which is confirmed by a second consecutive value obtained 3 or more weeks later. For patients with no PSA decline at Week 13, the PSA progression date is defined as the date that a $\geq 25\%$ increase and an absolute increase of ≥ 2 ng/mL above the baseline is documented.

Data for the analysis of primary endpoint TTPP1 will be cut-off if not less than 135 events of PSA progression occurred in association with the 1st line AAT.

After the discontinuation of the 1st line AAT due to PSA progression or other reasons, the 2nd line AAT will be started. Subjects who discontinued the 1st line AAT due to PSA

progression will start the 2nd line AAT within 6 weeks after the date of examination that identified PSA progression. Subjects who discontinued the 1st line AAT due to other reasons will start the 2nd line AAT within 6 weeks from the day when the investigator or sub-investigator decided the discontinuation.

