3.4 Criteria to Shift from 1st Line AAT to 2nd Line AAT

If any of the following is satisfied, the study drug will be shifted to the 2nd line AAT after the discontinuation of the 1st line AAT:

- 1. PSA progression
- 2. In case where the 1st line AAT is to be discontinued due to AEs, but the investigator or sub-investigator considers that there is no problem in the subject tolerance to transition to the 2nd line AAT
- 3. In case where the 1st line AAT is to be discontinued due to progression of disease other than PSA progression, but the investigator or sub-investigator considers that there is no problem in the subject tolerance to transition to the 2nd line AAT.

In any of the following cases, study treatment will be discontinued without shifting to the 2nd line AAT:

1. In case of enzalutamide as 2nd line AAT, subjects with seizure as an AE

- 2. In case of flutamide as 2nd line AAT, subjects with the latest AST or ALT exceeding the upper limit of normal
- 3. Other cases that the investigator or sub-investigator considers unsuitable for study continuation

4 **TREATMENT(S)**

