5.5.6 Follow-up of Adverse Events

All AEs occurring during or after the subject has discontinued the study are to be followed up until resolved or judged to be no longer clinically significant, or until they become chronic to the extent that they can be fully characterized.

If during AE follow-up, the AE progresses to an "SAE," or if a subject experiences a new SAE, the investigator must immediately report the information to the Sponsor.

Even if the subject does not return to normal or baseline level, and the investigator or subinvestigator judged follow-up survey is not necessary or will be completed, the reason for the judgment should be recorded in the source materials.

Please refer to Appendix 12.2 Liver Safety Monitoring and Assessment for detailed instructions on drug-induced liver injury (DILI).

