6.2 Safety Variables

Safety will be assessed by evaluation of the following variables:

- AEs (frequency, severity, seriousness, and relationship to study drug).
- Clinical laboratory variables (hematology, biochemistry including liver enzymes and total bilirubin, and urinalysis)
- Vital signs (systolic and diastolic blood pressure, pulse rate)
- **ECOG Performance Status**

AEs will be recorded from time of actually received the study drugs until the Safety Followup visit (28 days after the final treatment with the study drug, start date of cytocidal chemotherapy, or start date of new treatment for prostate cancer, whichever occurs first.). AEs will be assigned on treatment period (treatment arm) according to definition of treatment-emergent period in section 7.1.2. When assigning treatment arm cannot be judged due to starting date and/or end date of AE is missing, such AEs will be assigned on treatment depending on recorded CRF page. However, the AE that recorded as continues from 1st line AAT will be excluded from assignment of 2nd line AAT. TEAE is defined as an AEs observed within above treatment-emergent period or AEs that assigned the treatment arms. The severity of all AEs is to be evaluated by the investigator based on the National Cancer Institute's Common Terminology Criteria for Adverse Events (CTCAE) version 4.0.

A drug-related AE is defined as any AE with at least possible relationship to study treatment as assessed by the investigator or with missing assessment of the causal relationship.

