The treatment-emergent period will be defined as the period of time from the date of the first dose of study drug to 28 days after the date of the last dose of study drug, or 1 day prior to the date of initiation of cytotoxic chemotherapy for prostate cancer or an investigational agent treating prostate cancer, whichever occurs first. And 1st line treatment-emergent period is defined as the period of time from the date of the first dose of study drug in 1st line to 28 days after the date of the last dose of study drug in 1st line, or 1 day prior to the date of initiation of cytotoxic chemotherapy for prostate cancer or an investigational agent treating prostate cancer, whichever occurs first. Regarding 2nd line treatment-emergent period is applied same rule for 2nd line date.

• Baseline Value and Post-Baseline Value

Unless otherwise specified, the baseline value is defined as the last non-missing measurement prior to the randomization of study drug. When analysis be provided separately by treatment lines, baseline value for 2nd line AAT is defined as the last non-missing value measurement prior to the enrollment for 2nd line AAT of study drug.

Post-baseline value is defined as a measurement taken after the randomization of study drug. For Post-baseline value for 2nd line is defined as a measurement taken after enrollment during of study for 2nd line AAT.

Baseline value is defined as the last non-missing measurement prior to randomization (or register of 2nd line AAT) and post-baseline value is defined as a measurement taken after randomization for subjects who did not receive study drug. Change from baseline is defined as (post-baseline value - baseline value). Both date and time of drug administration and measurement should be considered when calculating baseline value. If time is not available, then date only should be used.

Treatment Group

Treatment group is defined as planned randomized treatment sequence which divide to initial enzalutamide 160 mg/day group or the initial flutamide 125 mg × 3 times daily (375 mg/day) group.

• Treatment Arm

Treatment arm is defined as administration drug group regardless 1st line or 2nd line treatment. That is enzalutamide plus ADT arm include subject who receive enzalutamide plus ADT at 1st line and 2nd line. Flutamide plus ADT include who receive flutamide plus ADT at 1st line and 2nd line.

• Treatment Line

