All analysis of safety will be presented by actual treatment group for SAF, unless specified otherwise. The last non-missing measurement prior to the first dose of study drug will be used as the baseline.

7.5.1 **Adverse Events**

The severity of all AEs is to be evaluated by the investigator based on the National Cancer Institute's CTCAE version 4.0. The coding dictionary for this study will be Medical Dictionary for Regulatory Activities (MedDRA) version 19.1. It will be used to summarize AEs by SOC and PT.

The safety analysis will be performed in the safety analysis set, and summarized by the time of assessment and by the treatment group that actually received the study drugs. The period of onset in the treatment period with the study drug is defined up to 28 days after the final treatment with the study drug, start date of cytocidal chemotherapy, or start date of new treatment for prostate cancer, whichever occurs first. Safety will be assessed by AEs, frequency of treatment discontinuation associated with AEs, and laboratory test value summary statistics. Descriptive statistics, and not inferential statistics, will be used.

The total number of AEs reported will be presented by treatment arm (i.e. enzalutamide v.s. flutamide) and overall total for the SAF. The same analysis will be provided dividing treatment lines. AEs which have occurred during 1st line AAT and 2nd line AAT will be included to analysis. In this 'event level' analyses, all AEs will be counted separately. The following categories will be presented:

- Number of AEs,
- Number of AEs leading to study drug discontinuation,
- Number of drug-related AEs,
- Number of drug-related AEs leading to study drug discontinuation,
- Number of grade 3 or higher AEs,
- Number of grade 3 or higher drug-related AEs,
- Number of serious adverse events (SAEs),

- Number of drug-related SAEs,
- Number of SAEs leading to study drug discontinuation,
- Number of drug-related SAEs leading to study drug discontinuation,
- Number of SAEs leading to death,
- Number of drug-related SAEs leading to death.

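### An adverse event that carries over from 1st line and worsens on the second drug may be missing from that drug's AE tables, because SAP 6.2 makes no exception for worsening

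*SAP*

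**What the plan says.** SAP 6.2 assigns each AE to a drug and line by the treatment-emergent windows of SAP 7.1.2. The 1st-line window runs from the first 1st-line dose to "28 days after the date of the last dose of study drug in 1st line", unless cytotoxic chemotherapy or an investigational agent for prostate cancer starts sooner. The 2nd-line window follows the same rule.

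A fallback applies "When assigning treatment arm cannot be judged due to starting date and/or end date of AE is missing": the CRF page on which the AE was entered then decides. The next sentence reads "However, the AE that recorded as continues from 1st line AAT will be excluded from assignment of 2nd line AAT". After that comes the definition: "TEAE is defined as an AEs observed within above treatment-emergent period or AEs that assigned the treatment arms".

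SAP 7.5.1, repeating Protocol 7.5, uses different language: "The period of onset in the treatment period with the study drug is defined up to 28 days after the final treatment". The tables in SAP 7.5.1 are by treatment arm (the drug, whichever line it was given in) and again by line.

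The protocol makes carry-over likely. Protocol 3.4 allows the switch "In case where the 1st line AAT is to be discontinued due to AEs" if the investigator sees no tolerance problem. Protocol 2.2.1 says "Subjects who discontinued the 1st line AAT due to other reasons will start the 2nd line AAT within 6 weeks" and sets no minimum gap. Protocol 3.4 keeps two problems out of 2nd line: AST or ALT above the normal limit before flutamide, and seizure before enzalutamide. No other AE is required to have resolved.

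**The concern.** The by-drug AE tables are the main vehicle for the safety comparison, which is a stated objective (Protocol 2.1.3). In a switching design, an AE that starts on drug 1 and is still present on drug 2 can be handled in three ways: always counted for drug 2, never counted, or counted only if it gets worse there. The third is the usual choice, and the SAP does not state it.

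If the AE is never counted, an event that became Grade 3, became serious or ended treatment on drug 2 is absent from drug 2's tables. If it is always counted, drug 2 is charged with every unresolved but unchanged AE. In either case the programmer has to decide, and the same event can end up under different drugs.

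**Working it through.** The plan gives no figure on this point, so there is nothing to reproduce. The check is to follow one event through the text: a single AE record of Grade 1 fatigue that starts on 1st-line enzalutamide, is ongoing at the switch, becomes Grade 3 on 2nd-line flutamide and ends it. Is it in flutamide's AE tables?

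1. **Arm cannot be judged because a date is missing, so the CRF page decides.**
   - On a 1st-line page: absent.
   - On a 2nd-line page and marked as continuing from 1st line: absent.
   - On a 2nd-line page and not marked: present.

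2. **Dated AE, presence reading (SAP 6.2 and 7.1.2).** It was observed inside the 2nd-line window, so it is present. So is every carried-over AE that did not change. If the exclusion sentence is taken to cover all AEs, a record marked as continuing is absent here too.

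3. **Dated AE, onset reading (SAP 7.5.1).** Onset was in 1st line, so it is absent.

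4. **A new dated record made at worsening.** It is present on either reading, unless it is marked as continuing and the exclusion is taken to cover all AEs.

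No reading uses worsening to decide. Three further passages bear on the result:

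- **Missing dates are not remote.** The fallback names a missing end date, which an unresolved AE lacks; this matters wherever presence in 2nd line has to be judged. Protocol 7.10 planned to impute AE dates so that AEs could be allocated to treatment. SAP 7.11.1 confines imputation to concomitant medication and radiotherapy.
- **No text requires a new record.** Protocol 5.5.6 ("If during AE follow-up, the AE progresses to an" SAE) speaks of the same AE progressing, and only for reporting to the sponsor.
- **The maximum-severity rule does not help.** SAP 7.5.1 counts a repeated AE once at its worst grade but does not say which drug receives a grade reached after the switch.

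The event is not lost from the report. It remains in enzalutamide's tables, the overall total and the listing of all AEs (Protocol 7.5.1). The 2nd-line discontinuation reason is in the disposition table (SAP 7.2.1). That table could therefore show an AE discontinuation on flutamide that the flutamide AE table lacks. If the record holds only the worst grade, enzalutamide's tables may carry the Grade 3.

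**The case against.** The strongest reply has four parts.

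- **The exclusion is narrow.** Its opening word ties it to the missing-date fallback. For dated AEs the formal definition is presence in the window, which counts the event. The onset sentence in SAP 7.5.1 mainly sets where the window ends. This is a fair reading. But it counts all unchanged carry-over as well, and SAP 7.5.1 still contradicts it.
- **The CRF may solve it.** The reference to CRF pages and to a continuing mark suggests line-specific pages, in which case the exclusion may only prevent double entry. The data specification document (SAP 7.11) and the CRF instructions (Protocol 8.1.5) are not available and may require a new record when the grade rises. This stands as a limit on the conclusion, although the SAP itself contains no such rule.
- **Attribution to the first drug is defensible.** Fatigue was reported as an adverse reaction in 25.3% on enzalutamide in the global phase 3 study (Protocol 1.2.2.3), and enzalutamide is eliminated slowly in animals (Protocol 1.2.1). Worsening soon after the switch may reflect the first drug. This stands, and is a reason to flag early worsening.
- **The information is visible elsewhere.** Besides the listings and disposition, there is the swimmer's plot for drug-related AEs by grade (SAP 7.4.4) and the laboratory shift tables by line (SAP 7.5.2). True, but none of these corrects the AE incidence tables.

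**Conclusion.** The point holds as a minor one. The SAP excludes continuing AEs from 2nd line with no exception for worsening, at least where dates are missing, and is ambiguous for dated AEs. A worsened, serious or treatment-ending event may therefore be missing from the second drug's tables. This assumes that sites did not enter worsening as a new AE and that no unseen document supplies a rule.

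The number of subjects affected cannot be derived: the documents give no rate of switching, of AEs ongoing at the switch or of worsening. Safety is descriptive only, and no efficacy result is affected.

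A reader might infer three stronger things that the documents do not support:

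- **Every worsened AE is dropped.** The presence reading counts a dated one, provided the exclusion is limited to missing-date cases.
- **Most assignment routes lose the event.** SAP 6.2 has one default, with two possible readings, and one fallback whose result depends on page and mark. Counting these as separate routes gives no meaningful proportion.
- **The overlap of the two windows measures the loss.** The 28-day tail and the absence of a minimum gap do let the windows overlap. But overlap concerns double attribution near the switch, and it disappears if the second study drug counts as a new prostate cancer treatment under SAP 7.5.1.

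**What to change.** Put one rule in SAP 6.2, applying to all AEs with or without complete dates:

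> *An AE continuing from 1st line is not counted in 2nd line unless, after the first 2nd-line dose, its CTCAE grade exceeds its grade at the switch (the last grade before the first 2nd-line dose), it becomes serious, or it leads to discontinuation or modification of the 2nd-line drug. It is then a 2nd-line TEAE at its 2nd-line grade.*

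The comparison must be with the grade at the switch, not the 1st-line peak. Take an AE at Grade 3 on drug 1, Grade 1 at the switch and Grade 3 again on drug 2. Against the peak, 3 does not exceed 3 and the worsening is missed; against the switch, 3 exceeds 1 and it is caught.

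Align the onset sentence in SAP 7.5.1 with this rule. Flag worsening within 28 days of the last 1st-line dose. Where the 2nd-line grade was not recorded, list the event as ongoing at the switch.

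The cost is SAP wording and limited programming where the AE record shows grade or outcome on 2nd line. Elsewhere only a listing is feasible: the SAP is dated 8 July 2020, after the planned study end of March 2020, so collection can hardly be changed. The downsides are that a worsened event appears once under each drug, and that early worsening may belong to the first drug, hence the flag.

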5.5.3 Criteria for Causal Relationship to the Study Drug

AEs that fall under either "Possible," "Probable," or "Not assessable" should be defined as "AEs whose relationship to the study drugs could not be ruled out."

Causal relationship to the study drug	Criteria for causal relationship
Not related	A clinical event, including laboratory test abnormality, with a temporal relationship to drug administration which makes a causal relationship improbable, and/or in which other drugs, chemicals or underlying disease provide plausible explanations.
Possible	A clinical event, including laboratory test abnormality, with a reasonable time sequence to administration of the drug, but which could also be explained by concurrent disease or other drugs or chemicals. Information on drug withdrawal may be lacking or unclear.
Probable	A clinical event, including laboratory test abnormality, with a reasonable time sequence to administration of the drug, unlikely to be attributed to concurrent disease or other drugs or chemicals, and which follows a clinically reasonable response on re-administration (rechallenge) or withdrawal (dechallenge).
Not assessable	A report suggesting an adverse reaction which cannot be judged because Information is insufficient or contradictory, and which cannot be supplemented or verified.

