7.5.1 Adverse Events

The severity of all AEs will be evaluated by the investigator or sub-investigator based on NCI-CTCAE version 4.0. AEs will be coded using the Medical Dictionary for Regulatory Activities (MedDRA). The number and percentage of AEs, SAEs, AEs leading to discontinuation, and AEs related to study drug will be summarized by system organ class, preferred term and treatment group. The number and percentage of AEs by severity will also be summarized. All AEs will be listed.

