The number and percentage of subjects experiencing AEs will be presented by treatment arm and overall total for the SAF. The same analysis will be provided dividing treatment lines. AEs which have occurred during 1st line AAT and 2nd line AAT will be included to analysis. In this 'subject level' analyses, multiple AEs within the same category for a particular subject will only be counted once and the denominator for the percentage calculation will be the number of subjects in the SAF. The following categories will be presented:

- Number and percentage of subjects with AEs,
- Number and percentage of subjects with AEs leading to study drug discontinuation,
- Number and percentage of subjects with drug-related AEs,
- Number and percentage of subjects with drug-related AEs leading to study drug discontinuation,
- Number and percentage of subjects with grade 3 or higher AEs,
- Number of grade 3 or higher drug-related AEs,
- Number and percentage of subjects with SAEs,
- Number and percentage of subjects with drug-related SAEs,
- Number and percentage of subjects with SAEs leading to study drug discontinuation,
- Number and percentage of subjects with drug-related SAEs leading to study drug discontinuation,
- Number and percentage of subjects with SAEs leading to death,
- Number and percentage of subjects with drug-related SAEs leading to death.

The number and percentage of subjects experiencing AEs will be tabulated by SOC, PT, treatment arm and overall total for the SAF. The same analysis will be provided dividing treatment lines. AEs which have occurred during 1st line AAT and 2nd line AAT will be included to analysis. For this and similar analyses, an AE will only be counted once for each subject if the same AE is experienced on more than one occasion. Tables will be sorted by descending overall total of SOC and PT frequency. The following summaries will be produced:

- AEs,
- AEs leading to study drug discontinuation,
- drug-related AEs,
- drug-related AEs leading to study drug discontinuation,
- grade 3 or higher AEs,
- SAEs,

- drug-related SAEs,
- SAEs leading to study drug discontinuation,
- drug-related SAEs leading to study drug discontinuation,
- SAEs leading to death,
- drug-related SAEs leading to death,
- TEAEs excluding serious adverse events that equal to or exceed a threshold of 2.0% in any treatment group, and
- Common TEAEs that equal to or exceed a threshold of 2.0% in any treatment group.

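### SAP 6.2 leaves AEs rated Not assessable out of its drug-related definition, although Protocol 5.5.3 groups them with Possible and Probable

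*SAP*

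**What the plan says.** Protocol 5.5.3 sets four causality ratings: Not related, Possible, Probable and Not assessable. The last three form one group, labelled "AEs whose relationship to the study drugs could not be ruled out". The Not assessable row has its own description, which begins "A report suggesting an adverse reaction which cannot be judged because Information is insufficient or contradictory". This is the only rule in the protocol for grouping causality ratings. Protocol 7.5.1 then plans that "AEs leading to discontinuation, and AEs related to study drug will be summarized by system organ class, preferred term and treatment group", without pointing back to 5.5.3.

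SAP 6.2 defines a drug-related AE as "any AE with at least possible relationship to study treatment as assessed by the investigator or with missing assessment of the causal relationship". It does not list the four ratings, and no other part of the SAP says how Not assessable is handled.

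SAP 7.5.1 uses the term throughout. Examples are "Number of drug-related SAEs leading to death" at event level and "Number and percentage of subjects with drug-related AEs" at subject level. It also appears in the tables by system organ class and preferred term and in those by maximum severity. The swimmer plot in SAP 7.4.4 marks drug-related AEs as well.

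**The concern.** The SAP rule has two ways in: a rating of Possible or higher, or no rating at all. Not assessable meets neither. The rule is therefore cautious when the investigator recorded nothing. It is not cautious when the investigator recorded a suspected reaction that could not be resolved. The second case carries more evidence of a possible drug effect than a blank field does, so the ordering is hard to defend.

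Comparing the safety of the two regimens is a stated objective of the trial. The safety analysis is descriptive, so the drug-related counts are themselves the result, with no model or test behind them. A reader of the study report would expect those counts to follow the protocol's grouping. Under the literal SAP rule they would not, and SAP 6.2 gives no reason for the departure.

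**Working it through.** The documents state no figure that this point depends on, so the check compares two definitions.

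**Step 1: each possible content of the causality field under each rule.**

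| Causality field | Protocol 5.5.3 group (not ruled out) | SAP 6.2 drug-related, read literally |
|---|---|---|
| Not related | no | no |
| Possible | yes | yes |
| Probable | yes | yes |
| Not assessable | yes | no |
| Blank | not addressed | yes |

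The protocol's set less the SAP's set is {Not assessable}. The SAP's set less the protocol's set is {missing}.

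**Step 2: direction.** Two comparisons have to be kept apart.

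- Against a rule that keeps Possible, Probable, Not assessable and missing, the literal SAP count is lower by exactly the number of AEs rated Not assessable.
- Against the protocol's literal group, the SAP count differs by (number missing − number Not assessable). Neither number is given, so the sign of this net difference is unknown.

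**Step 3: size at event level.** The share rated Not assessable is not in the documents. I assume that it is between 0% and 10% of the AEs in the protocol's group. For every 100 such AEs, the literal SAP rule keeps 100 × (1 − share), before any missing ratings are added:

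| Assumed share | Kept of 100 |
|---|---|
| 0% | 100 |
| 1% | 99 |
| 2% | 98 |
| 5% | 95 |
| 10% | 90 |

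**Step 4: size at subject level.** One reclassified subject moves a percentage by 100/n points, where n is the denominator.

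- First-line tables: n is about 100 per group (planned enrolment), so 100/100 = 1 point.
- Tables by treatment arm: SAP 7.1.2 puts everyone who receives a drug in either line into that drug's arm. If nearly all subjects cross over, n approaches 100 + 100 = 200, so 100/200 = 0.5 point.
- Second-line tables: n is the number who shift, which the documents do not give. The step exceeds 1 point if fewer than 100 do.

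SAP 7.5.1 counts a subject once per category. The row therefore moves only if the subject has no other related AE in it.

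**The case against.** The best reply is that the SAP is silent on Not assessable, and silence is not exclusion. The SAP introduces itself as an elaboration of the protocol's analysis, so the protocol's grouping might be taken to carry over. The author may also have meant a missing assessment to include an AE that the investigator could not assess. Neither reading is impossible, but the text supports neither. The SAP states a closed rule, and a populated causality field would ordinarily be programmed as non-missing. That two programmers could code it differently is itself a reason to amend.

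Several limits do stand:

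- A reader might infer that the protocol counts these AEs as related. Its label is that a relationship could not be ruled out. The link to the related-AE table in Protocol 7.5.1 is natural but inferred.
- A reader might infer that drug-related totals will certainly fall short of the protocol's. Step 2 shows that the net sign is unknown, because the SAP adds missing ratings. That addition may offset the total, but it does not restore the omitted events.
- In the background studies, adverse reactions occurred in 63.2%, 69.3% and 65.0% of enzalutamide subjects (phase 2 part in Japan, overseas phase 3, global phase 3). The row for any drug-related AE would therefore often not move.
- No event is hidden. All AEs, grade 3 or higher AEs, SAEs, AEs leading to discontinuation and SAEs leading to death are also tabulated regardless of causality, and Protocol 7.5.1 lists all AEs.
- SAP 7.5.1 states that "Descriptive statistics, and not inferential statistics, will be used". The primary endpoint, the sample size and every test are untouched.

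**Conclusion.** The mismatch is real and should be corrected. As written, SAP 6.2 omits a recorded rating that Protocol 5.5.3 groups with Possible and Probable, and it treats a blank field more cautiously than that rating.

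The loss is conditional. It occurs only if at least one AE is rated Not assessable and the rule is programmed literally. It is confined to descriptive safety outputs. The expected scale is about 0.5 to 1 percentage point per reclassified subject in the pooled and first-line tables, and zero where the subject already has a related AE in the row. This rests on planned enrolment of 100 per group and on the extent of crossover.

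It is tempting to go further and say that the rating will fall mainly on unexplained deaths, or that a few cases could empty the drug-related SAE or death rows. The documents do not support this. They give no frequency for the rating and do not say which events attract it. Protocol 5.5.3 reserves it for reports that cannot be completed or checked. The SAE reporting and AE follow-up duties in Protocol 5.5.5 and 5.5.6 would tend to keep its use low.

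**What to change.** Replace the definition in SAP 6.2 with: *A drug-related AE is any AE assessed as Possible, Probable or Not assessable (Protocol 5.5.3), or with missing causality.* Apply it to all drug-related tables in SAP 7.5.1, to the swimmer plot, and to related-event listings, including the flutamide-related listing in SAP 7.9.

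The cost is one sentence and one line of derivation code. Drug-related counts may rise slightly. If no AE carries the rating, nothing changes. If the SAP can no longer be amended, the same definition can be used and justified in the clinical study report, as SAP section 1 allows.
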